10.6.4.2 Female Participants who Become Pregnant

- The Investigator will collect pregnancy information on any female participant who becomes pregnant while participating in this study. Information will be recorded on the appropriate form and submitted to the Sponsor within 24 hours of learning of a participant's pregnancy. The participant will be followed to determine the outcome of

the pregnancy. The Investigator will collect follow-up information on the participant and the neonate and the information will be forwarded to the Sponsor. Generally, follow-up will not be required for longer than 6 to 8 weeks beyond the estimated delivery date. Any termination of pregnancy will be reported, regardless of fetal status (presence or absence of anomalies) or indication for the procedure.

- While pregnancy itself is not considered to be an AE or SAE, any pregnancy complication or elective termination of a pregnancy will be reported as an AE or SAE. A spontaneous abortion is always considered to be an SAE and will be reported as such. Any post-study pregnancy-related SAE considered reasonably related to the study intervention by the Investigator will be reported to the Sponsor as described in [Section 8.3.5](#). While the Investigator is not obligated to actively seek this information in former study participants, he or she may learn of an SAE through spontaneous reporting.
- Any female participant who becomes pregnant while participating in the study will discontinue study intervention.

[figure not shown]
10.7 APPENDIX 7: GENETICS

Use/Analysis of DNA

- Genetic variation may impact a participant's response to study intervention, susceptibility to, and severity and progression of disease. Variable response to study intervention may be due to genetic determinants that impact immune response, drug absorption, distribution, metabolism, and excretion; mechanism of action of the drug; disease etiology; and/or molecular subtype of the disease being treated. Therefore, where local regulations and IRB/IEC allow, a blood and tumor sample will be collected for DNA analysis from consenting participants.
- DNA samples will be used for research related to checkpoint inhibitor therapy or cancer and/or immune disorders and related diseases or evaluation of new assay technologies. They may also be used to develop tests/assays including diagnostic tests related to checkpoint inhibitor therapies and cancer. Genetic research may consist of the analysis of one or more candidate genes or the analysis of genetic markers throughout the genome or analysis of the entire genome (as appropriate).
- DNA samples may be analyzed for whole genome sequencing and relationship to clinical outcomes in response to study intervention. Additional analyses may be conducted if it is hypothesized that this may help further understand the clinical data.
- The samples may be analyzed as part of a multi-study assessment of genetic factors involved in the response to checkpoint inhibitor therapy or study interventions of this class to understand study disease or related conditions.
- The results of genetic analyses may be reported in the clinical study report or in a separate study summary.
- The Sponsor will store the DNA samples in a secure storage space with adequate measures to protect confidentiality.
- The samples will be retained while research on checkpoint inhibitor therapy continues in accordance with applicable law.

GI Adverse Event Management Algorithm

Rule out non-inflammatory causes. If non-inflammatory cause is identified, treat accordingly and continue I-O therapy.
Opiates/narcotics may mask symptoms of perforation. Infliximab should not be used in cases of perforation or sepsis.

[figure not shown]

Patients on IV steroids may be switched to an equivalent dose of oral corticosteroids (eg, prednisone) at start of tapering or earlier, after sustained clinical improvement is observed. Lower bioavailability of oral corticosteroids should be taken into account when switching to the equivalent dose of oral corticosteroids.

* Discontinue for Grade 4 diarrhea or colitis. For Grade 3 diarrhea or colitis, 1) Nivolumab monotherapy: Nivolumab can be delayed. 2) Nivolumab+ ipilimumab combination: ipilimumab should be discontinued while nivolumab can be delayed. Nivolumab monotherapy can be resumed when symptoms improve to Grade 1. Please refer to protocol for dose delay and discontinue criteria for other combinations.

Hepatic Adverse Event Management Algorithm

Rule out non-inflammatory causes. If non-inflammatory cause, treat accordingly and continue I-O therapy. Consider imaging for obstruction.

[figure not shown]
Patients on IV steroids may be switched to an equivalent dose of oral corticosteroids (e.g. prednisone) at start of tapering or earlier, after sustained clinical improvement is observed. Lower bioavailability of oral corticosteroids should be taken into account when switching to the equivalent dose of oral corticosteroids.

^A Please refer to protocol dose delay and discontinue criteria for specific details.

*The recommended starting dose for AST or ALT > 20 x ULN or bilirubin >10 x ULN is 2 mg/kg/day methylprednisolone IV.

Endocrinopathy Adverse Event Management Algorithm

[figure not shown]
Rule out non-inflammatory causes. If non-inflammatory cause, treat accordingly and continue I-O therapy.
Consider visual field testing, endocrinology consultation, and imaging.

Patients on IV steroids may be switched to an equivalent dose of oral corticosteroids (eg, prednisone) at start of tapering or earlier, after sustained clinical improvement is observed. Lower bioavailability of oral corticosteroids should be taken into account when switching to the equivalent dose of oral corticosteroids.

Skin Adverse Event Management Algorithm

Rule out non-inflammatory causes. If non-inflammatory cause, treat accordingly and continue I-O therapy.

[figure not shown]
Patients on IV steroids may be switched to an equivalent dose of oral corticosteroids (e.g. prednisone) at start of tapering or earlier, after sustained clinical improvement is observed. Lower bioavailability of oral corticosteroids should be taken into account when switching to the equivalent dose of oral corticosteroids.

*Refer to NCI CTCAE v5 for term-specific grading criteria.

**If Steven-Johnson Syndrome (SJS), toxic epidermal necrosis (TEN), Drug Reaction with Eosinophilia and Systemic Symptoms (DRESS) is suspected, withhold I-O therapy and refer patient for specialized care for assessment and treatment. If SJS, TEN, or DRESS is diagnosed, permanently discontinue I-O therapy.

Neurological Adverse Event Management Algorithm

Rule out non-inflammatory causes. If non-inflammatory cause, treat accordingly and continue I-O therapy.

[figure not shown]

Patients on IV steroids may be switched to an equivalent dose of oral corticosteroids (eg. prednisone) at start of tapering or earlier, after sustained clinical improvement is observed. Lower bioavailability of oral corticosteroids should be taken into account when switching to the equivalent dose of oral corticosteroids.

^aDiscontinue for any grade myasthenia gravis, Guillain-Barre syndrome, treatment-related myelitis, or encephalitis.

Pulmonary Adverse Event Management Algorithm

[figure not shown]
Rule out non-inflammatory causes. If non-inflammatory cause, treat accordingly and continue I-O therapy. Evaluate with imaging and pulmonary consultation.

Patients on IV steroids may be switched to an equivalent dose of oral corticosteroids (eg, prednisone) at start of tapering or earlier, after sustained clinical improvement is observed. Lower bioavailability of oral corticosteroids should be taken into account when switching to the equivalent dose of oral corticosteroids.

Renal Adverse Event Management Algorithm

[figure not shown]
Rule out non-inflammatory causes. If non-inflammatory cause, treat accordingly and continue I-O therapy.

Patients on IV steroids may be switched to an equivalent dose of oral corticosteroids (eg, prednisone) at start of tapering or earlier, after sustained clinical improvement is observed. Lower bioavailability of oral corticosteroids should be taken into account when switching to the equivalent dose of oral corticosteroids.

Myocarditis Adverse Event Management Algorithm

Rule out non-inflammatory causes. If non-inflammatory cause, treat accordingly and continue I-O therapy.

Patients on IV steroids may be switched to an equivalent dose of oral corticosteroids (eg, prednisone) at start of tapering or earlier, after sustained clinical improvement is observed. Lower bioavailability of oral corticosteroids should be taken into account when switching to the equivalent dose of oral corticosteroids. Prophylactic antibiotics should be considered in the setting of ongoing immunosuppression.

10.9

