AEs associated with nivolumab with or without ipilimumab exposure may represent an immunologic etiology. These irAEs may occur shortly after the first dose or several months after the last dose of treatment and may affect more than one body system simultaneously. Therefore, early recognition and initiation of treatment is critical to reduce complications. Based on existing clinical study data, drug-related AEs have included pulmonary toxicity, renal toxicity (including acute renal failure), endocrine abnormalities, gastrointestinal toxicity, dermatologic toxicity (including rash), and hepatotoxicity. For nivolumab monotherapy and combination therapy, the majority of these AEs have been managed successfully with supportive care and, in more severe cases, a combination of dose delay, permanent discontinuation, and/or use of corticosteroids or HRT (endocrinopathies). For suspected irAEs, ensure adequate evaluation to confirm etiology or exclude other causes. Additional procedures or tests such as bronchoscopy, endoscopy, and skin biopsy may be included as part of the evaluation.

For Amendments 1 and 2, dose modification and toxicity management guidelines for irAEs associated with nivolumab with or without ipilimumab are provided in [Table 7](#). For Amendment 3+ (advanced prostate cohorts), requirements for the discontinuation of study treatment for irAEs associated with nivolumab with or without ipilimumab are provided in [Table 9](#).

Table 7: Dose Modification and Toxicity Management Guidelines for Adverse Events Associated with Nivolumab with or without Ipilimumab

Drug-Related Adverse Event (AE) per CTCAE V5	Severity	Action Taken	Clarifications, Exceptions, and Resume Criteria
Gastrointestinal			
Colitis or Diarrhea	Grade 2	Delay dose	Dosing may resume when AE resolves to baseline
	Grade 3	Nivolumab monotherapy: Delay dose	Dosing may resume when AE resolves to baseline
		When administered with ipilimumab: Permanently Discontinue Ipilimumab	Nivolumab monotherapy may be resumed when AE resolves to baseline. If Grade 3 diarrhea or colitis recurs while on nivolumab monotherapy, permanently discontinue
	Grade 4	Permanently discontinue	
Renal			
Serum Creatinine Increased	Grade 2 or 3	Delay dose	Dosing may resume when AE resolves to Grade \leq 1 or baseline value
	Grade 4	Permanently discontinue	
Pulmonary			
Pneumonitis	Grade 2	Delay dose	Dosing may resume after pneumonitis has resolved to \leq Grade 1.
	Grade 3 or 4	Permanently discontinue	

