If 3 or fewer of the first 5 participants in the ipilimumab 5 mg/kg cohort (Prostate Cohort B) experience a TRAE leading to discontinuation of both agents, an additional 10 participants will be enrolled to receive nivolumab 1 mg/kg Q3W and ipilimumab 5 mg/kg Q6W for 2 cycles, then nivolumab maintenance 480 mg Q4W until PD or intolerable toxicity (Prostate Cohort B). If 4 or more of the first 5 participants of the ipilimumab 5 mg/kg cohort (Prostate Cohort B) experience a TRAE leading to discontinuation of both agents, an additional 10 participants will be enrolled to receive nivolumab 1 mg/kg Q3W and ipilimumab 3 mg/kg Q6W for 2 cycles, then nivolumab maintenance 480 mg Q4W until PD or intolerable toxicity (Prostate Cohort A). Only TRAEs leading to treatment discontinuation of both agents occurring up until the 5th participant in each cohort completes Cycle 1 will be included—dose delays for adverse events not otherwise meeting criteria at that time will not be counted. The stopping rule was chosen as this

corresponds to a > 80% chance that the toxicity rate in the cohort is > 40%, assuming a beta (0.8, 1.2) prior.

If either prostate cohort demonstrates 8 or greater TRAEs requiring discontinuation of therapy at any time, enrollment will be suspended until an ad hoc safety review convenes and provides a recommendation, as described above.

Table 9: Toxicity Criteria Requiring Permanent Treatment Discontinuation of Both Nivolumab and Ipilimumab (Amendment 3+ Advanced Prostate Cohort Only)

Participants should be monitored for the occurrence of any of the following AEs that are considered by the Investigator to be possibly, probably, or definitely related to ipilimumab, nivolumab, or the immunotherapy combination.
 
Treatment with all study intervention should be monitored for the occurrence of any of the following TRAEs, and if any of these events occur, action should be taken as follows:

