
• Any Grade 2 drug-related uveitis, eye pain or blurred vision that does not respond to topical therapy and does not improve to Grade 1 severity within the re-treatment period OR requires systemic treatment.• Any Grade 3 non-skin, drug-related AE lasting > 7 days, or recurs with the following exceptions for laboratory abnormalities, diarrhea, colitis, neurologic toxicity, drug-related uveitis, pneumonitis, bronchospasm, hypersensitivity reactions, infusion reactions, and endocrinopathies:
○ Grade 3 drug-related diarrhea, colitis, neurologic toxicity, uveitis, pneumonitis, bronchospasm, myocarditis, hypersensitivity reaction, or infusion reaction of any duration requires discontinuation.○ Grade 3 drug-related endocrinopathies, adequately controlled with only physiologic hormone replacement do not require discontinuation. Adrenal insufficiency requires discontinuation regardless of control with hormone replacement.○ Grade 3 drug-related laboratory abnormalities do not require treatment discontinuation except:
▪ Grade 3 drug-related thrombocytopenia > 7 days or associated with bleeding requires discontinuation.▪ Any drug-related liver function test abnormality that meets the following criteria require discontinuation:
• Grade ≥ 3 drug-related AST, ALT or total bilirubin requires discontinuation.
○ In most cases of Grade 3 AST, ALT evaluation study drug(s) will be permanently discontinued. If the investigator determines a possible favorable benefit/risk ratio that warrants continuation of study drug(s), a discussion between the investigator and the Medical Monitor (or designee) must occur.• Concurrent AST or ALT > 3x ULN and total bilirubin > 2x ULN.• Any Grade 4 drug-related adverse event or laboratory abnormality (including but not limited to creatinine, AST, ALT, or total bilirubin), except for the following events which do not require discontinuation:
○ Grade 4 neutropenia ≤ 7 days.○ Grade 4 lymphopenia or leukopenia or asymptomatic amylase or lipase.○ Isolated Grade 4 electrolyte imbalances/abnormalities that are not associated with clinical sequelae and are corrected with supplementation/appropriate management within 72 hours of their onset.○ Grade 4 drug-related endocrinopathy adverse events, such as, hyper- or hypothyroidism, or glucose intolerance, which resolve or are adequately controlled with physiologic hormone replacement (corticosteroids, thyroid hormones) or glucose-controlling agents, respectively, may not require discontinuation after discussion with and approval from the Medical Monitor (or designee).• Any event that leads to delay in dosing lasting > 12 weeks from the previous dose requires discontinuation, with the following exceptions:
○ Dosing delays to allow for prolonged steroid tapers to manage drug-related adverse events are allowed.

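### The Appendix 8 footnote on Grade 3 colitis or diarrhea conflicts with Table 7 for metastatic participants and with Table 9 for prostate participants

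*Protocol*

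**What the plan says.** Three places in the protocol deal with Grade 3 colitis or diarrhea on the combination.

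- **Table 7 (Section 6.6.1.1).** The action is "When administered with ipilimumab: Permanently Discontinue Ipilimumab". On nivolumab it says "Nivolumab monotherapy may be resumed when AE resolves to baseline", and it adds "If Grade 3 diarrhea or colitis recurs while on nivolumab monotherapy, permanently discontinue". Its scope is set just above the table: "For Amendments 1 and 2, dose modification and toxicity management guidelines for irAEs associated with nivolumab with or without ipilimumab are provided in" Table 7.
- **Appendix 8, gastrointestinal algorithm footnote.** "Nivolumab+ ipilimumab combination: ipilimumab should be discontinued while nivolumab can be delayed", followed by "Nivolumab monotherapy can be resumed when symptoms improve to Grade 1". The footnote then sends the reader to the protocol, but only for combinations other than this one. It states no cohort or amendment limit.
- **Table 9 (Section 6.6.1.4).** "Grade 3 drug-related diarrhea, colitis, neurologic toxicity, uveitis, pneumonitis, bronchospasm, myocarditis, hypersensitivity reaction, or infusion reaction of any duration requires discontinuation". The table's title says that it concerns permanent discontinuation of both agents and applies only to the Amendment 3+ prostate cohort. Section 6.6.1.1 assigns it the same scope.

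Section 6.6 introduces the Appendix 8 algorithms as an aid to investigators, without restricting them to a cohort. Section 4.3.2.1, the dose rationale for Prostate Cohorts A and B, cites Appendix 8 as the source of treatment guidance for immune-related events.

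**The concern.** An investigator who treats this event can find two instructions that apply to the same participant and disagree. In the metastatic portion they disagree on when nivolumab may restart. In the prostate cohorts they disagree on whether it may restart at all. Sites could therefore re-treat differently after an important toxicity of the combination.

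There is also a link to safety monitoring. The Prostate Cohort B rule in Section 6.6.1.4 counts treatment-related events that lead to both agents being stopped. The count in the first 5 participants decides which cohort receives the next 10. If a site stops ipilimumab only and later resumes nivolumab, the event might be left out of that count.

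**Working it through.** **1. Appendix 8 against Table 7 (metastatic participants).** Both stop ipilimumab and both allow nivolumab later. They differ in the restart condition: improvement to Grade 1 against resolution to baseline. For a participant whose baseline was Grade 1 the two coincide. For one whose baseline was Grade 0, Appendix 8 permits a restart at Grade 1 and Table 7 does not. Table 7 also has a recurrence clause that the readable Appendix 8 text lacks.

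**2. Appendix 8 against Table 9 (prostate participants).** Appendix 8 delays and then resumes nivolumab; Table 9 stops both agents whatever the duration. No participant can be managed under both. Section 6.6.1 also says in general terms, in a paragraph that covers prostate dosing, that participants who stop ipilimumab early for toxicity may go on to nivolumab maintenance. It makes no exception for Table 9 events.

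**3. Does Appendix 8 yield to the tables?** Not for this event. The hepatic algorithm footnote in the same appendix defers to the protocol's delay and discontinuation criteria. The gastrointestinal footnote states its own rule for this combination and defers only for others.

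**4. Table 7 against Table 9.** Section 6.6.1.1 gives them to different populations, so their difference is not a contradiction.

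**5. The Prostate Cohort B count.** Inputs from Section 6.6.1.4: prior beta(0.8, 1.2), 5 participants, reference rate 0.40, threshold 4 of 5, stated justification a probability above 80%. After x events the posterior is beta(0.8 + x, 1.2 + 5 − x).

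- x = 3: beta(3.8, 3.2), P(rate > 0.40) = 0.776
- x = 4: beta(4.8, 2.2), P(rate > 0.40) = 0.942

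Four is the smallest count above 0.80, so the plan's own rule is reproduced. If one of four qualifying events is recorded as stopping ipilimumab only, the count becomes 3 of 5, and the next 10 participants go to Cohort B instead of Cohort A.

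**6. Which events are counted?** Section 6.6.1.4 begins by describing events that necessitate stopping both agents and cites Table 9. The decision sentences that follow count events that lead to stopping both. The sentence citing Table 9 counts the required action; the decision sentences can be read as counting the action taken. SAP Section 4.4 uses both expressions too and does not cite Table 9.

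**7. TOX in the metastatic arms.** Section 8.3.7 defines TOX by a related event leading to treatment discontinuation in the initial 12 weeks. The stopping rule in Section 9.3.1.1 is stated for the metastatic arms, where Table 9 plays no part. Table 7 and Appendix 8 both stop ipilimumab. Whether that alone counts as TOX is unclear, but equally so under either text. The restart condition could change TOX status only for a participant who stays at Grade 1 above a Grade 0 baseline and for that reason never resumes nivolumab.

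**The case against.** The strongest case on the other side is that the cohort tables govern. Section 6.6.1.1 calls Table 9 a set of requirements, and Section 6.6 offers Appendix 8 only as assistance. A prostate site that resumed nivolumab under Appendix 8 would then be departing from a requirement, not choosing between equal rules. Section 6.6.1.4 also ties the Cohort B assessment to Table 9. It excludes dose delays only where the event does not otherwise meet the criteria, and a Grade 3 drug-related colitis does meet them. Much of this stands, and it makes a miscount less likely. It does not remove the conflict: no sentence says that the tables prevail over Appendix 8, and the prostate rationale sends readers to the appendix.

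A reader might infer that the protocol holds three competing rules for one participant, or that safety stopping in general depends on which page a site opened. The documents do not support either. Tables 7 and 9 have separate stated populations, which leaves one mismatch per cohort. The clinician-facing app in Section 8.8 does bring Table 7 into the prostate cohort, but its output is advisory. The TOX rule is barely touched.

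Two limits come from the text as available. The algorithm figure is not shown, so only its footnote could be compared. Table 7 footnote b, which allows resumption at Grade 0 or 1, has no visible marker. If it belongs to the colitis row, Table 7 carries both conditions and the inconsistency with baseline lies inside Table 7 as well.

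**Conclusion.** The inconsistency is real and the text is wrong as written, but it is a small point of wording. The unscoped Appendix 8 footnote contradicts Table 7 on the restart condition for metastatic participants with a Grade 0 baseline. It contradicts Table 9 on whether nivolumab may restart for Amendment 3+ prostate participants. The main consequence is inconsistent re-treatment after a serious immune toxicity.

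The effect on the Cohort B rule is possible but conditional. It needs a site to follow Appendix 8 in place of Table 9, the event to be counted by the action taken, and the count to sit at the threshold. The figures 0.776 and 0.942 show what any single event does in a group of 5; they do not measure how often this conflict would matter, which the documents do not allow one to estimate. The effect on TOX is minor. No view is taken here on which rule is clinically right.

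**What to change.** Reconcile Appendix 8 with Table 7 and Table 9 so that each cohort has one stated rule for this event, and have the gastrointestinal footnote refer to the table for that cohort. State whether Table 7 footnote b applies to the colitis or diarrhea row. In Section 6.6.1.4 and SAP Section 4.4, say whether the Cohort B rule counts events that meet Table 9 or events after which both agents were actually stopped. The choice of rule is the sponsor's. The cost is wording only, in an amendment or administrative letter; the sample size, data collection and analysis methods do not change.
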